# **13.7** Baseline Characteristics and Demographics

Baseline characteristics will be assessed by the use of tables and/or graphs for each cohort separately. No statistical hypothesis tests will be performed on these characteristics. The number and percentage of participants screened, randomized, the primary reasons for screening failure, and the primary reason for discontinuation will be displayed. Demographic variables (e.g., age, gender), baseline characteristics, primary and secondary diagnoses, and prior and concomitant therapies will be summarized by treatment either by descriptive statistics or categorical tables

# **13.8** Compliance (Medication Adherence)

A day within the study will be considered an On-Therapy day if the participant receives the study medication/Placebo infusion. The number of Days Should be on Therapy is the total number of days from the first day of study medication to the date of the last dose of study medication. For each participant, percent compliance will then be calculated using the following formula:

Percent Compliance = (Number of Days Should be on Therapy/Number of Days on Therapy) x 100

Summary statistics will be provided on percent compliance by treatment group for the FAS population.

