Temozolomide	(PO or IV) Initial dose of 150mg/m2 once daily for 5 consecutive days per 28-day treatment cycles, may be increased to 200mg/m2 once daily for 5 consecutive days in the following 28-day treatment cycles
Temozolomide metronomic	(PO) 50mg/m2 once daily continuously
Bevacizumab or Biosimilar	(IV) 10mg/kg every 2 weeks

Table 1: Investigator's Choice Single Agent Standard of Care Treatments.

After recovering from surgery, participants will be evaluated every 6 weeks with radiographic imaging to assess response to treatment. The Response Assessment in Neuro-Oncology (RANO) criteria will be used as the efficacy endpoint of response rate. A modified RANO (iRANO) (as described in Section 11.4) will be used to evaluate response and progression in an exploratory fashion due to the tumor response patterns seen with immunotherapy treatment (e.g., tumor flare). Adverse events will be monitored throughout the trial and graded in severity according to the guidelines outlined in the NCI CTCAE version 5.0. Treatment with study therapy will continue until documented disease progression supported by two consecutive time points of tumor growth, unacceptable adverse event(s), intercurrent illness that prevents further administration of treatment, investigator's decision to withdraw the participant, participant withdraws consent, pregnancy of the participant, noncompliance with trial treatment or procedure requirements, completion of 24 months of study therapy, or administrative reasons. After the end of treatment, each participant will be followed for 30 days for adverse event monitoring and 90 days for serious adverse event reporting. Participants who discontinue treatment for reasons other than disease progression will have post-treatment follow-up of disease status approximately every 8 weeks until disease progression, withdrawing consent, or becoming lost to follow-up. All participants will be followed by telephone contact or medical record review for overall survival until death, withdrawal of consent, or the end of the study, whichever comes first.

The investigator shall take responsibility for and shall take all steps to maintain appropriate records and ensure appropriate supply, storage, handling, distribution and usage of trial treatments in accordance with the protocol and any applicable laws and regulations.

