### 6. DOSE DELAY

For patients who experience an adverse event possibly related to VB-111 and are scheduled for a repeat dose, the repeat dose will be delayed until they meet the criteria outlined in Section 5.2. No dose modifications are allowed.

For patients who experience an adverse event related to standard of care and are scheduled for a repeat dose, the repeat dose will be delayed until they meet the criteria outlined in Section 5.2. Dose reductions are permitted for standard of care therapies, at the discretion of the Investigator. We suggest up to two dose-reductions by 20% for each standard of care therapy.

Dosing interruptions are permitted in the case of medical/surgical events or logistical reasons not related to study therapy (e.g., elective surgery, unrelated medical events, participant vacation, and/or holidays). Participants should be placed back on study therapy within 3 weeks of the scheduled interruption, unless otherwise discussed with the Overall Principal Investigator, [name], or his designee. The reason for interruption should be documented in the participant's study record.

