## **13.2** Definitions of Analysis Sets

- The Full Analysis Set (FAS) population will serve as the population for the analysis of primary efficacy endpoint TIL density in this study. The FAS population consists of all participants within each cohort who have received a preoperative dose of VB-111/placebo and had a surgery.
- The intention to treat (ITT) population is defined as all randomized participants. The ITT population will be used for secondary efficacy endpoints (PFS6, OS).
- The All Participants as Treated (APaT) population will be used for the analysis of safety data in this study. The APaT population consists of all allocated participants who received at least one dose of study treatment. At least one laboratory or vital sign measurement obtained subsequent to at least one dose of study treatment is required for inclusion in the analysis of each specific parameter. To assess change from baseline, a baseline measurement is also required.

A randomized, placebo controlled phase II, surgical trial to evaluate early immunologic pharmacodynamic parameters for the viral cancer therapy ofranergene obadenovec (VB-111) in patients with surgically accessible recurrent/progressive glioblastoma Version 3.0 February 18, 2021

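### The percent-compliance ratio in section 13.8 is inverted and divides calendar days by infusion days, so on-schedule Group A participants would score thousands of percent

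*Combined protocol and SAP*

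**What the plan says.** Section 13.8 gives the formula "Percent Compliance = (Number of Days Should be on Therapy/Number of Days on Therapy) x 100" and defines both of its terms.

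- The actual term: "A day within the study will be considered an On-Therapy day if the participant receives the study medication/Placebo infusion". It is therefore a count of infusion days.
- The planned term "is the total number of days from the first day of study medication to the date of the last dose of study medication". It is therefore a span of calendar days. Placebo is named in the first definition but not in this one.

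For reporting: "Summary statistics will be provided on percent compliance by treatment group for the FAS population". Section 13.2 defines that set: "The FAS population consists of all participants within each cohort who have received a preoperative dose of VB-111/placebo and had a surgery".

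The infusion schedule comes from sections 5.3.2 and 5.8 and from footnotes 6 and 27 of the study calendar (section 10). All groups have one pre-operative infusion 21±7 days before surgery. Groups A and B then have VB-111 starting 28-35 days after surgery and repeated every 6 weeks, with treatment for up to 24 months.

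Section 6 allows the schedule to slip. After an adverse event possibly related to VB-111, "the repeat dose will be delayed until they meet the criteria outlined in Section 5.2". For unrelated or logistical interruptions, "Participants should be placed back on study therapy within 3 weeks of the scheduled interruption", unless otherwise discussed with the Overall Principal Investigator.

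No other section gives a different compliance formula.

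**The concern.** Compliance is normally what was taken as a share of what was due, with 100% meaning full adherence. This formula puts what was due on top, so fewer infusions over the same period give a higher figure. The terms also do not measure the same thing. With one infusion about every six weeks, nearly every day in the span is not an infusion day, even for a participant who misses nothing. In addition, the span ends at the last dose actually received, so doses due after it leave no trace.

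At stake is one prespecified descriptive table. Programmed as written, its values could not be read as adherence, and they would not rank participants by adherence in either direction.

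**Working it through.** **Starting point.** The plan states no expected compliance value, so there is no figure to reproduce. The formula is evaluated directly on the plan's own schedule, using Group A because its pre-operative infusion is VB-111 and clearly starts the span.

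**Inputs and formula.** Let n be the total number of infusions and g the days from the pre-operative dose to the first post-operative dose.

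- g runs from 14 + 28 = 42 to 28 + 35 = 63 days.
- The last dose falls on day L = g + 42 × (n − 2).
- Score = 100 × L/n, or 100 × (L + 1)/n if both end days are counted. Section 13.8 does not say which.
- The plan gives no expected n. Taking 24 months as 730 days from the first post-operative dose, the most is 2 + floor(730/42) = 19.

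**Full adherence, Group A, strict 42-day cycles.**

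| n | Lowest (g = 42, end days not both counted) | Highest (g = 63, both counted) |
|---|---|---|
| 2 | 100 × 42/2 = 2,100% | 100 × 64/2 = 3,200% |
| 5 | 100 × 168/5 = 3,360% | 100 × 190/5 = 3,800% |
| 10 | 100 × 378/10 = 3,780% | 100 × 400/10 = 4,000% |
| 19 | 100 × 756/19 = 3,979% | 100 × 778/19 = 4,095% |

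If the 24 months run from the pre-operative dose, n is at most 18 (g = 42) or 17 (g = 63), and the top score is 100 × 694/17 = 4,082%. Applying the ±3-day window of footnote 27 to the whole span moves the extremes to 100 × 39/2 = 1,950% and 100 × 780/19 = 4,105%. With a single infusion the score is 0% or 100%, depending only on how days are counted.

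**Direction.** Assume doses due on days 0, 52, 94, 136 and 178, with both end days counted.

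- All five given: 100 × 179/5 = 3,580%.
- A middle dose skipped: 100 × 179/4 = 4,475%.
- The final dose missed: 100 × 137/4 = 3,425%.

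One missed dose moves the score up or down according to which dose it was.

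**Swapping the terms.** Full adherence then gives between 100 × 19/778 = 2.4% and 100 × 2/42 = 4.8%. The unit mismatch remains.

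**Delays permitted under section 6.** Assume post-operative doses at days 0, 63 and 126, that is, two interruptions of 21 days. With the pre-operative dose there are 4 infusions over 42 + 126 = 168 to 63 + 126 = 189 days, giving 100 × 168/4 = 4,200% to 100 × 189/4 = 4,725%.

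**Group B.** If placebo starts the span, Group B scores as Group A does. If the span definition is read literally, it starts at the first VB-111 dose while the placebo day stays in the denominator. Two infusions then give 0/2 = 0% or 1/2 = 50%. Nineteen give 100 × 714/19 = 3,758% or 100 × 715/19 = 3,763%.

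**Group C.** If neither placebo nor standard of care is study medication, the span has no start date. If standard of care counts, infusion days depend on the agent and route chosen from Table 1.

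**Replacement ratio.** Infusions received over infusions due gives 5/5 = 100% in the five-dose example. It gives 4/5 = 80% for either missed dose, provided treatment had not been discontinued before that dose fell due. For the participant with two permitted interruptions, a fixed 42-day grid has post-operative doses due on days 0, 42, 84 and 126, giving 3/4 = 75%. With due dates moved, it gives 3/3 = 100%.

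**The case against.** The best case for leaving this alone is that nothing depends on it. Percent compliance enters no endpoint, test or analysis set. Section 13.9 reports cycles with an infusion, section 13.7 reports reasons for discontinuation, and a value in the thousands of percent would be noticed on first output. That limits the importance of the point but does not make the formula right. The obvious repair at that stage, swapping the terms, would still give a wrong table.

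Four stronger readings are tempting, and the documents do not support them.

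- A reader might apply the range of about 2,100% to 4,100% to Group B as well. The span definition omits placebo, so Group B can score 0% or 50% with two infusions.
- A reader might take about 4,100% as a ceiling. Section 6 permits delays that push an otherwise adherent participant above it.
- A reader might say that bevacizumab is the only Table 1 option with infusion days. Table 1 also allows temozolomide by the intravenous route, so no single Group C figure can be given.
- A reader might infer that a planned comparison between groups is spoiled. Section 13.8 plans summary statistics by group and no test. Different post-operative regimens would limit comparability under any formula.

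A fair criticism of the replacement also stands. Section 6 permits interruptions for reasons as broad as vacation, so if all of these move the due date, few infusions will count as missed and the ratio may sit near 100%.

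**Conclusion.** The formula is wrong as written on two counts: the ratio is inverted, and it divides calendar days by infusion days. Both follow from section 13.8 itself and need no assumption.

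The size is illustrative. It assumes Group A, full adherence, strict 42-day cycles and 2 to 19 infusions. The start of the 24 months and the day-count convention matter little once there are two or more infusions. Group B and C scores cannot be fixed until the plan says whether placebo and standard of care are study medication.

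The consequence is confined to one descriptive table. It is worth correcting before that table is programmed, and it does not bear on the primary, secondary or safety conclusions.

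**What to change.** Replace the formula in section 13.8 with: Percent Compliance = (VB-111/placebo infusions received / VB-111/placebo infusions due per protocol up to treatment discontinuation) × 100. Then state:

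- that a delay permitted under section 6 moves the due date and is not a missed infusion;
- whether the pre-operative placebo counts. Every participant in the FAS has had the pre-operative infusion, so counting it adds one to both terms;
- how Group C standard of care is handled. If it is left out and placebo is counted, every Group C participant in the FAS scores 1/1 = 100% and that column carries no information.

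This is an analysis rule only and changes no dosing rule. The cost is a wording change, modest programming, and classifying each interruption as permitted or not. The last item is not free. Section 6 places the reason for an interruption in the participant's study record, and Table 7 shows only when the treatment form is due, not whether it captures the reason. Section 13 provides for changes to non-confirmatory analyses to be listed and explained in the clinical study report.

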# **13.9** Extent of Exposure

Extent of Exposure for a participant is defined as number of cycles in which the participant receives

the study medication infusion. Summary statistics will be provided on Extent of Exposure for APaT population.

#### 13.10 Procedure for Accounting for Missing, Unused and Spurious Data

Missing data will be indicated in the listings, but excluded from all descriptive analyses. All data will be listed, including otherwise unused data. Spurious data will be identified as such, wherever possible.

## **14. PUBLICATION PLAN**

This trial is intended for publication, even if terminated prematurely. Publication may include any or all of the following: posting of a synopsis online, abstract and/or presentation at a scientific conference, or publication of a full manuscript. The Sponsor-Investigator will work with the authors and VBL to submit a manuscript describing trial results within 12 months after the last data become available, which may take up to several months after the last participant visit in some cases. The Overall Principal Investigator will post a synopsis of trial results for approved products on www.clinicaltrials.gov by 12 months after the last participant's last visit for the primary outcome, 12 months after the decision to discontinue development, or product marketing (dispensed, administered, delivered or promoted), whichever is later.

These timelines may be extended for products that are not yet marketed, if additional time is needed for analysis, to protect intellectual property, or to comply with confidentiality agreements with other parties. Authors of the primary results manuscript will be provided the complete results from the Clinical Study Report, participant to the confidentiality agreement. When a manuscript is submitted to a biomedical journal, the Sponsor's policy is to also include the protocol which includes the statistical analysis plan to facilitate the peer and editorial review of the manuscript. If the manuscript is subsequently accepted for publication, the Sponsor will allow the journal, if it so desires, to post on its website the key sections of the protocol that are relevant to evaluating the trial, specifically those sections describing the trial objectives and hypotheses, the participant inclusion and exclusion criteria, the trial design and procedures, the efficacy and safety measures, the statistical analysis plan, and any amendments relating to those sections. VBL and the Sponsor reserves the right to redact proprietary information.

Authorship credit should be based on 1) substantial contributions to conception and design, or acquisition of data, or analysis and interpretation of data; 2) drafting the article or revising it critically for important intellectual content; and 3) final approval of the version to be published. Authors must meet conditions 1, 2 and 3. Significant contributions to trial execution may also be taken into account to determine authorship, provided that contributions have also been made to all three of the preceding authorship criteria. Although publication planning may begin before conducting the trial, final decisions on authorship and the order of authors' names will be made based on participation and actual contributions to the trial and writing, as discussed above. The first author is responsible for defending the integrity of the data, method(s) of data analysis and the scientific content of the manuscript.

The Sponsor-Investigator and VBL must have the opportunity to review all proposed abstracts, manuscripts or presentations regarding this trial 45 days prior to submission for publication/presentation. Any information identified by the Sponsor or VBL as confidential must

A randomized, placebo controlled phase II, surgical trial to evaluate early immunologic pharmacodynamic parameters for the viral cancer therapy of ranergene obadenovec (VB-111) in patients with surgically accessible recurrent/progressive glioblastoma Version 3.0 February 18, 2021

be deleted prior to submission; this confidentiality does not include efficacy and safety results. Sponsor review can be expedited to meet publication timelines.

# APPENDIX A: KARNOFSKY PERFORMANCE STATUS

A randomized, placebo controlled phase II, surgical trial to evaluate early immunologic pharmacodynamic parameters for the viral cancer therapy ofranergene obadenovec (VB-111) in patients with surgically accessible recurrent/progressive glioblastoma Version 3.0 February 18, 2021

APPENDIX B: MULTI-CENTER DATA AND SAFETY MONITORING PLAN

# DFCI IRB Protocol #: 19-792

Dana-Farber/Harvard Cancer Center Multi-Center Data and Safety Monitoring Plan

## **1.0 INTRODUCTION**

The Dana-Farber/Harvard Cancer Center Multi-Center Data and Safety Monitoring Plan (DF/HCC DSMP) outlines the procedures for conducting a DF/HCC Multi-Center research protocol. The DF/HCC DSMP serves as a reference for any sites external to DF/HCC that are participating in a DF/HCC clinical trial.

## 1.1 Purpose

To establish standards that will ensure that a Dana-Farber/Harvard Cancer Center Multi-Center protocol will comply with Federal Regulations, Health Insurance Portability and Accountability Act (HIPAA) requirements and applicable DF/HCC Standard Operating Procedures.

## 1.2 Multi-Center Data and Safety Monitoring Plan Definitions

**DF/HCC Multi-Center Protocol**: A research protocol in which one or more outside institutions are collaborating with Dana-Farber/Harvard Cancer Center where a DF/HCC investigator is the sponsor. DF/HCC includes Dana-Farber/Partners Cancer Care (DF/PCC) Network Clinical Trial Affiliates.

**Lead Institution:** One of the Dana-Farber/Harvard Cancer Center consortium members (Dana-Farber Cancer Institute (DFCI), Massachusetts General Hospital (MGH), Beth Israel Deaconess Medical Center (BIDMC), Boston Children's Hospital (BCH), Brigham and Women's Hospital (BWH)) responsible for the coordination, development, submission, and approval of a protocol as well as its subsequent amendments per the DFCI IRB and applicable regulatory guidelines (CTEP, Food and Drug Administration (FDA), Office of Biotechnology Activities (OBA) etc.). The Lead Institution is typically the home of the DF/HCC Sponsor. The Lead Institution also typically serves as the Coordinating Center for the DF/HCC Multi-Center Protocol.

**DF/HCC Sponsor:** The person sponsoring the submitted Multi-Center protocol. Within DF/HCC, this person is the Overall Principal Investigator who takes responsibility for initiation, management and conduct of the protocol at all research locations. In applicable protocols, the DF/HCC Sponsor will serve as the single liaison with any regulatory agencies (i.e. FDA, etc.). The DF/HCC Sponsor has ultimate authority over the protocol and is responsible for the conduct of the study at DF/HCC and all Participating Institutions. In most cases the DF/HCC Sponsor is the same person as the DF/HCC Overall Principal Investigator; however, both roles can be filled by two different people.

**Participating Institution:** An institution that is outside the DF/HCC and DF/PCC consortium that is collaborating with DF/HCC on a protocol where the sponsor is a DF/HCC Investigator. The Participating Institution acknowledges the DF/HCC Sponsor as having the ultimate authority and responsibility for the overall conduct of the study.

**Coordinating Center:** The entity (i.e. Lead Institution, Medical Monitor, Contract Research Organization (CRO), etc) that provides administrative support to the DF/HCC Sponsor in order that s/he may fulfill the responsibilities outlined in the protocol document and DSMP, and as specified in applicable regulatory guidelines (i.e. CTEP Multi-Center Guidelines). In general, the Lead Institution is the Coordinating Center for the DF/HCC Multi-Center Protocol.

**DF/HCC Office of Data Quality (ODQ):** A group within DF/HCC responsible ensuring high-quality standards are used for data collection and the ongoing management of clinical trials, auditing, and data and safety monitoring. ODQ also coordinates quality assurance efforts related to multi-center clinical research.

**DF/HCC** Research Informatics for Operations (RIO): A group within DF/HCC responsible for providing a comprehensive data management platform for managing clinical trial data.

## 2.0 GENERAL ROLES AND RESPONSIBILITIES

For DF/HCC Multi-Center Protocols, the DF/HCC Sponsor, the Coordinating Center, and the Participating Institutions are expected to adhere to the following general responsibilities:

#### 2.1 DF/HCC Sponsor

The DF/HCC Sponsor, [name], will accept responsibility for all aspects of conducting a DF/HCC Multi-Center protocol which includes but is not limited to:

- Oversee the coordination, development, submission, and approval of the protocol as well as subsequent amendments.
- Ensure that the investigators, study team members, and Participating Institutions are qualified and appropriately resourced to conduct the protocol.
- Include the Multi-Center Data and Safety Monitoring Plan as an appendix to the protocol.
- Ensure all Participating Institutions are using the correct version of the protocol.
- Ensure that each participating investigator and study team member receives adequate protocol training (and/or a Site Initiation Visit prior to enrolling participants) and throughout trial's conduct as needed.
- Ensure the protocol will be provided to each participating site in a language understandable to all applicable site personnel when English is not the primary language.
- Monitor progress and overall conduct of the study at all Participating Institutions.
- Ensure all DFCI Institutional Review Board (IRB), DF/HCC and other applicable (i.e. FDA) reporting requirements are met.
- Review data and maintain timely submission of data for study analysis.
- Act as the single liaison with FDA (investigator-held IND trials), as applicable.

- Ensure compliance with all requirements as set forth in the Code of Federal Regulations, applicable DF/HCC requirements, HIPAA requirements, and the approved protocol.
- Commit to the provision that the protocol will not be rewritten or modified by anyone other than the DF/HCC Sponsor.
- Identify and qualify Participating Institutions and obtain accrual commitments prior to extending the protocol to that site.
- Monitor accrual and address Participating Institutions that are not meeting their accrual requirements.

